## 4 Protocol synopsis

### 4.1 Brief summary

The purpose of this study is to assess the feasibility of a smart phone application (app)-based intervention to reduce risks from wildfire smoke among young adults with asthma. We will pilot test two interventions, both based on the EPA's Smoke Sense phone app compared to a control group. We will recruit 60 young adults aged 18-26 with asthma and randomize them to 1 of 3 groups for a 3-month study period during wildfire season. The long-term goal is to minimize asthma exacerbations from exposure to wildfire smoke. Our aims are to:

1. Establish the feasibility (recruitment, enrollment, retention rates), acceptability (intervention engagement, fidelity, usability, research attitude), and barriers and facilitators of adopting the technology of the Smoke Sense interventions and use of portable devices in young adults with asthma.
2. Explore the preliminary impact of the Smoke Sense interventions on lung function and asthma control. These primary outcomes will be assessed using objective measures (spirometry) and validated, self-report tools. Secondary outcomes will be anxiety, exposure reduction behaviors (e.g. stayed indoors, wore a mask), and symptom mitigating behaviors (use of medication, unscheduled health care appointments), measured via self-report and a Global Positioning System device. Outcome by group will be summarized. Preliminary evidence of treatment effect and its variance will be examined for a future clinical trial.
3. Explore potential mediators (medication adherence, self-management skills, stress) and moderators (asthma severity/control) of the interventions to asthma outcomes.

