Participants will fill out a series of questionnaires via a link sent to their phone. The RA will weigh and measure the participant. The RA will train the participant on the use of a portable digital spirometer with a mouthpiece that connects to the participant's smartphone. The participant will download spirometry software onto their phone and enter their age, sex, height and weight. Participants will be asked to practice exhaling into the mouthpiece. This air turns a motor while the device registers the speed, adapts it and transfers the measurement to the participants' smartphone application. When a participant initiates exhalation, a chronometer changes from red to green after 6 seconds of exhalation. Users can visualize their exhalation curve via the color change and see if they have made an error. The device will select the best result out of 3 attempts. Participants will be asked to return-demonstrate the process until they have definitive results. No calibration is required. Participants will also receive a GPS device and will be instructed on its continuous use during waking hours. Participants will be told that they will be sent an email with a link to a suite of Qualtrics' surveys, which they will be asked to complete via their phone at T2, T3 and T4. Participants in both intervention groups will be instructed on how to download and use the Smoke Sense app. Participants will be asked to return to the clinical lab so research personnel can download their GPS data at T2, T3 and T4. At T4 they will return their spirometer and GPS unit, and complete the System Usability Scale and the Research Attitudes Questionnaire. They can earn \$150, in \$50 increments, per visit, T2-T4.

This study proposes 2 intervention groups: Smoke Sense and Smoke Sense Plus. Smoke Sense Plus offers potentially value-added preventive activities to Smoke Sense. We hypothesize that with these additional activities, users will take actions to reduce their exposure before experiencing symptoms and reduce the severity of outcomes.

Upon downloading, the Smoke Sense mobile app prompts users to set up a Profile, which includes a zip code, demographic information (sex, age, race, education level), baseline health information (pre-existing conditions, physical activity level, time spent outdoors), and beliefs about smoke and air pollution (e.g. Does smoke impact health?). In the Symptoms & Smoke

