**Missing data.** If the assumption of “missing at random” can be safely satisfied, GLMM appropriately uses maximum likelihood methods to handle missing data. If this assumption is not satisfied, sensitivity analyses will be performed to examine the impact of different assumptions (e.g. missing not at random) on intervention effects.

**Program Feasibility, Fidelity and Impact.** Program feasibility will be determined by whether or not the rates of recruitment, enrollment, retention in the study (outlined in the Sample Size justification, below) are met. Intervention acceptability will be determined by a high level of engagement with, and adherence to, the Smoke Sense and Smoke Sense Plus interventions. Acceptability of the portable devices used in data collection will be measured using the System Usability Scale, and the Research Attitude Scale.

**Sample Size Justification.** The choice of sample size (n=60) was based on achieving Aim 1, focusing on assessment of the feasibility and acceptability of the Smoke Sense interventions. **Feasibility.** We expect that the true consent rate of eligible young adults is 75%. To test this, we will recruit up to 86 eligible individuals. There is an 89% probability that 60 or more of these individuals will consent to participate if the true consent rate is 75% (based on the cumulative binomial probability). We expect that the true rate of completion of the T3 assessment is 80%. If this is correct, there is an 87% probability that we will observe at least 45 out of 60 participants completing the T3 assessment. Similarly, we expect that the true rate of completion of the T4 assessment is 75%. If this is correct, there is an 85% probability that we will observe at least 42 out of 60 participants completing the T4 assessment. **Acceptability.** We hypothesize that the true intervention adherence rate for the two intervention groups, Smoke Sense and Smoke Sense Plus, is 70% and 85%, respectively. If this is correct, there is an 87% probability that we will observe that at least 12 out of 20 participants will adhere to Smoke Sense. There is a 93% probability that we will observe that at least 15 out of 20 participants will adhere to Smoke Sense Plus.

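### Device usability and research attitude are scored only at T4, so 20–25% of participants are expected to have no score and device acceptability may be overstated

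*Combined protocol and SAP*

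**What the plan says.** **Timing.** Section 4.2.a places both scales at the final visit, when the equipment is handed back: "At T4 they will return their spirometer and GPS unit, and complete the System Usability Scale". The Research Attitudes Questionnaire follows in the same sentence. Survey links also go to participants' phones at T2 and T3, but the two scales are not listed there, and nothing is described for people who leave early.

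**Role.** Section 4.4 (Program Feasibility, Fidelity and Impact) states: "Acceptability of the portable devices used in data collection will be measured using the System Usability Scale", and names the research attitude scale beside it. Aim 1 in section 4.1 lists "acceptability (intervention engagement, fidelity, usability, research attitude", so the two scales supply two of four components. The acceptability of the interventions is judged separately: "Intervention acceptability will be determined by a high level of engagement with, and adherence to, the Smoke Sense and Smoke Sense Plus interventions".

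**Expected completion.** Section 4.4 (Sample Size Justification) says "we expect that the true rate of completion of the T4 assessment is 75" per cent, and that "there is an 85% probability that we will observe at least 42 out of 60 participants completing the T4 assessment". For the preceding visit it expects 80%, and says that "there is an 87% probability that we will observe at least 45 out of 60 participants completing the T3 assessment".

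**Missing data.** The missing-data text in section 4.4 relies on likelihood estimation in the mixed models, with sensitivity analyses directed at intervention effects. The analytic plan also compares, descriptively, those who drop out early with those who finish.

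**The concern.** A scale asked once, at the end, is seen only in people who get to the end. The burdens that the scales are meant to capture are wearing a GPS unit through waking hours, using a spirometer and returning to the laboratory. These are also plausible reasons for leaving. If they are, the least satisfied participants are the ones without a score.

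The plan has no way to recover those scores. A mixed model uses a participant's earlier values on the same outcome, and here there are none. Comparing the characteristics of dropouts and completers shows who left, not how they rated the devices. Controls do not receive the app, so these scales are the only acceptability measure stated for them.

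At stake is the pilot's evidence on whether the devices can be carried into a larger trial. If loss related to device burden differs by arm, the comparison of device scores between arms is affected as well.

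**Working it through.** **1. The plan's own figures.** These are exact binomial upper tails.
- T4: P(X ≥ 42 | n = 60, p = 0.75) = 0.851. The plan states 85%; reproduced.
- T3: P(X ≥ 45 | n = 60, p = 0.80) = 0.869. The plan states 87%; reproduced.

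**2. Participants expected to have no score.** Number missing = 60 × (1 − completion rate).

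| Completion | Source | Scored | Missing |
|---|---|---|---|
| 80% | one of two week-8 rates in 4.2.a; T3 rate in 4.4 | 48 | 12 (20%) |
| 75% | the other week-8 rate in 4.2.a; T4 rate in 4.4 | 45 (about 15 per arm) | 15 (25%) |
| 70% | the T4 benchmark of 42 of 60 | 42 | 18 (30%) |

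In the last row the retention benchmark counts as met while 30% have no device score.

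The first two rows reflect a conflict in the documents. Section 4.2.a attaches both 80% and 75% to week 8. Section 4.4 attaches them to T3 and T4. The model description in 4.4 has only three timepoints, the third at 8 weeks. The calendar time of T4 is therefore unclear, but on either rate 20–25% are expected to be missing.

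**3. Bias of the completers' mean.** Let m be the missing fraction and d the mean score of completers minus the mean that non-completers would have given. The mean over all randomized is (1 − m) × completer mean + m × (completer mean − d), so the completers' mean is too high by m × d.

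The documents give no value for d. The values below are assumptions in SD units.

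| d (assumed) | m = 0.20 | m = 0.25 | m = 0.30 |
|---|---|---|---|
| 0 | 0 | 0 | 0 |
| 0.5 SD | 0.10 SD | 0.125 SD | 0.15 SD |
| 1 SD | 0.20 SD | 0.25 SD | 0.30 SD |

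If d is negative, the sign reverses and acceptability is understated.

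**4. Bounds that assume no direction.** Suppose 36 of 45 completers (80%, assumed) rate the devices acceptable. The plan sets no such cut-off, so this is only an illustration. Over all 60, the proportion lies between 36/60 = 60% (no non-completer agrees) and (36 + 15)/60 = 85% (all agree). The reported 80% could be 20 points too high or 5 points too low.

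**5. What an earlier administration recovers.** At 80% T3 completion, about 48 of 60 would have at least one score if everyone scored at T4 was also scored at T3. That is 3 of the 15 expected to be missing, with 12 still unscored. No completion rate is given for T2, so its yield cannot be computed. If participants who leave do not return, it is at least as large as at T3.

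**The case against.** A reader might infer that acceptability as a whole is measured only in completers. The documents do not support that. Engagement and adherence decide intervention acceptability, and the adherence benchmarks use full arms: at an expected 70%, "there is an 87% probability that we will observe that at least 12 out of 20 participants will adhere to Smoke Sense", and for Smoke Sense Plus 15 of 20 at an expected 85%. App data can be tied to the study ID from set-up, without a T4 visit.

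A reader might also infer that acceptability will certainly look better than it is. The documents give no reasons for dropout and no value for d, so they support only that it may be overstated. Nor does the problem reach the sample size: that rests on consent, completion and adherence, and no scale score, cut-off or precision target enters it.

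Three further points can be made for the plan.
- Asking at device return is a sensible time for an end-of-use rating. This stands, and the T4 score should be kept.
- Loss driven by burden would lower retention, which is itself a feasibility criterion in Aim 1, and dropouts are to be compared with completers. Readers would therefore see attrition beside the device scores. This helps interpretation but supplies none of the missing ratings.
- The summaries are descriptive and come from a pilot. This limits the consequence but does not remove the selection.

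**Conclusion.** The point holds for device usability and research attitude. Both are scheduled only at T4, and by the plan's own rates about 12 to 15 of 60 participants would have no score, or 18 at the retention benchmark. No provision in the plan covers that gap.

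The resulting bias is the missing fraction times an unknown difference. At 25% loss it is 0.125 SD if non-completers would score 0.5 SD lower, 0.25 SD if they would score 1 SD lower, zero if there is no difference, and in the opposite direction if they would score higher. Overstatement is plausible because device burden may drive dropout, but it is not demonstrated. No stated feasibility or adherence benchmark changes. The change is worth making because it is cheap and because the views of those who leave are hard to obtain afterwards.

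**What to change.** 1. Add both scales to a survey link already sent at T2 or T3. T2 is likely to reach more of those who later leave.
2. Offer both scales by link at early withdrawal.
3. Keep the T4 score as the end-of-use summary. Report scores by timepoint and for withdrawals, each with the number scored out of all randomized by arm.
4. Add a sensitivity summary that includes non-completers' earlier or exit scores. A last-available score should not become the main result: it carries early impressions forward and mixes them with end-of-use ratings.
5. Label T4 results as describing those who reached T4. Reconcile the timepoint labels and the two week-8 completion rates across sections 4.2.a and 4.4.

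**Cost.** One survey becomes slightly longer and one withdrawal link is needed; no visit is added. The gap narrows but does not close, because people lost before the earlier survey, or who simply stop responding, may still have no score.

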#### 4.2.d. Study phase

N/A or “OTHER” This is a behavioral intervention

#### 4.2.e. IVN study model: Parallel

#### 4.2.f. Masking: Investigator

#### 4.2.g: Randomized

### 4.3 Outcome measures

#### Primary: Lung function

Repeated assessment throughout the 8 week intervention and follow up period.

**Lung function** indicates future risk of adverse outcomes and is regularly monitored in people with asthma. Spirometry is used to objectively measure and monitor airway obstruction by blowing into a machine and measuring forced expiratory volume (FEV1), forced vital capacity (FVC), and their ratio (FEV1/FVC). A low FEV1, <60% predicted, is a potentially modifiable independent risk factor for severe asthma exacerbations. Portable spirometers, that are used by patients independently and connect to smartphones, have been validated against conventional spirometry performed by specialists in clinical settings.

#### Primary: Asthma Control Test

Repeated assessment throughout the 8 week intervention and follow up period.

The **Asthma Control Test (ACT)** measures the frequency of shortness of breath and general asthma symptoms, use of rescue medications, effect of asthma on daily functioning, and an overall self-assessment of asthma control via self-report. It has 5 items, uses a 4 week recall on symptoms and daily functioning and has a response scale that ranges from 5 (poor control) to 25 (complete control). ACT score >19 indicates well-controlled (versus 19 or < poorly controlled) asthma. The Minimally Important Difference (MID) is 3 points between two groups or for changes over time.

### 4.4 Statistical Design and Power

**Data management.** Spirometry and questionnaire (via Qualtrics) data will be captured through apps installed on the participants’ smartphone. GPS data will be downloaded at T2, T3 and T4 from the device. GPS data will be uploaded to the Urbanova cloud where it will be processed, cleansed, and de-identified. All other data will be sent directly to Urbanova for processing, de-identification, and integration.

**Analytic plan.** Feasibility, acceptability, and study outcomes (both primary and secondary) will be compared among the 3 study groups using descriptive statistics. Categorical and continuous data will be summarized as frequencies (percentages) and means (standard deviations [SDs]), respectively. Graphical displays and confidence intervals (CIs) will also be used to characterize group differences. Pursuant to Aim 1, descriptive statistics will be used to examine recruitment and retention rates, and characteristics of participants (Table 2 measures) who dropout early to those who complete the study. The primary outcomes for Aims 2 and 3 include lung function (FEV1, FVC and FEV1/FVC ratio measured by spirometry), asthma control (ACT), and asthma quality of life (Juniper’s AQLQ score averaging across items by domain and overall). To explore the preliminary impact of the Smoke Sense interventions on these primary outcomes (Aim 2), changes in means (SDs) across study timepoints will be examined for ceiling and floor effects,

restrictions in range and achievement of MID for each outcome. Generalized linear mixed models (GLMMs) will be fit that include main effects for study group and time point (1=baseline, 2=4 weeks, T3=8 weeks) and the interaction. An identity (continuous outcome) or logit (binary outcome) link function will be specified using SAS 9.4 PROC GLMMIX. Correlations within-participant over repeated measures of time will be controlled for using a random intercept model and a variance component covariate structure. The interaction terms and the slope coefficients for the 3 study groups will be of central interest to characterize changes in each of the outcomes across time. The same analytic approaches will be applied to the secondary (self-report) outcomes including anxiety, exposure reduction behaviors, and mitigating behaviors. Objective measures of exposure reduction behaviors will be estimated using GPS data. To examine the association between each of the GPS-based behaviors and study group during periods of poor AQ, full factorial GLMMs will be fit that include group, day, AQ (1=poor or worse, 0=normal) and specify a random intercept model with an autoregressive covariance structure.

Analyses will examine if the efficacy of the Smoke Sense interventions on outcomes is mediated (adherence to medication therapy, level of self-management skills, and psychological stress) or moderated (asthma severity/control) (Aim 3). For the mediation analyses, PROC CAUSALMED will be used for bootstrapping the CIs of the indirect effects or p-values for the corresponding tests. For moderation by asthma severity/control, we will run the same set of analyses proposed for Aim 2, now including an additional main effect of asthma severity/control and an interaction term of asthma severity/control by study group. We will graph the means of each outcome across subgroups to better understand what, if any, interaction is present. For Aims 2 and 3, two-sided statistical tests will be performed (alpha=0.05). The results from all of the statistical tests performed in Aims 2 and 3 will be interpreted as hypothesis-generating for a future R01 grant submission.

**Missing data.** If the assumption of “missing at random” can be safely satisfied, GLMM appropriately uses maximum likelihood methods to handle missing data. If this assumption is not satisfied, sensitivity analyses will be performed to examine the impact of different assumptions (e.g. missing not at random) on intervention effects.

**Program Feasibility, Fidelity and Impact.** Program feasibility will be determined by whether or not the rates of recruitment, enrollment, retention in the study (outlined in the Sample Size justification, below) are met. Intervention acceptability will be determined by a high level of engagement with, and adherence to, the Smoke Sense and Smoke Sense Plus interventions. Acceptability of the portable devices used in data collection will be measured using the System Usability Scale, and the Research Attitude Scale.

**Sample Size Justification.** The choice of sample size (n=60) was based on achieving Aim 1, focusing on assessment of the feasibility and acceptability of the Smoke Sense interventions. **Feasibility.** We expect that the true consent rate of eligible young adults is 75%. To test this, we will recruit up to 86 eligible individuals. There is an 89% probability that 60 or more of these individuals will consent to participate if the true consent rate is 75% (based on the cumulative binomial probability). We expect that the true rate of completion of the T3 assessment is 80%. If this is correct, there is an 87% probability that we will observe at least 45 out of 60 participants completing the T3 assessment. Similarly, we expect that the true rate of completion of the T4 assessment is 75%. If this is correct, there is an 85% probability that we will observe at least 42 out of 60 participants completing the T4 assessment. **Acceptability.** We hypothesize that the true intervention adherence rate for the two intervention groups, Smoke Sense and Smoke Sense Plus, is 70% and 85%, respectively. If this is correct, there is an 87% probability that we will observe that at least 12 out of 20 participants will adhere to Smoke Sense. There is a 93% probability that we will observe that at least 15 out of 20 participants will adhere to Smoke Sense Plus.

**Potential problems and alternative strategies.** Age could be broadened if recruitment is a challenge. If AQ is uncharacteristically healthy during the study period, we will use WSU-

Extension to recruit in areas with poor AQ. Data collection may influence behavior change. To examine this, we will assess matched outcomes among national Smoke Sense users and our control group. While not feasible in this study, we will include a future attention control group. Use of spirometry may decrease the magnitude of the interventions' effect. However, the benefits of measuring lung function objectively outweigh the potential decrease in effect sizes.

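### The continuous Aim 2 model does not adjust for the T1 value and forces one correlation and one variance on all visits, which costs precision and leaves its standard errors resting on an unchecked assumption

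*Combined protocol and SAP*

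**What the plan says.** Section 4.4 (Analytic plan) states that the Aim 2 models "will be fit that include main effects for study group and time point (1=baseline, 2=4 weeks, T3=8 weeks) and the interaction". Within-person correlation is handled "using a random intercept model and a variance component covariate structure". No baseline covariate is named, and the arms are not constrained to a common baseline mean. On the target, the plan says: "The interaction terms and the slope coefficients for the 3 study groups will be of central interest". Tests are two-sided at 0.05 and labelled hypothesis-generating.

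Four other statements bear on the point.

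- Section 4.1 gives the use of the results: "Preliminary evidence of treatment effect and its variance will be examined for a future clinical trial".
- Section 4.4 also plans descriptive work, in which "changes in means (SDs) across study timepoints will be examined for ceiling and floor effects".
- Section 4.3 (Asthma Control Test) sets a threshold that applies to change: "The Minimally Important Difference (MID) is 3 points between two groups or for changes over time".
- The separate model for daily GPS data will "specify a random intercept model with an autoregressive covariance structure".

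**The concern.** Two features of the model matter for identity-link outcomes at the three coded visits.

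First, with baseline as a response and a free mean per arm, each group-by-time term is a difference between arms in change from baseline. Baseline is subtracted in full, whatever its correlation with the later value. Regression on baseline gives a more precise group difference, and the gain grows as the correlation falls.

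Second, a random intercept with variance components has two covariance parameters. It makes the baseline-to-week-8 correlation equal the baseline-to-week-4 correlation, and it makes the variance the same at every visit. If either restriction is wrong, the model-based standard errors (SEs) of individual contrasts can be wrong, including those of the slopes and interaction terms that the plan puts at the centre. At stake are the length and coverage of the Aim 2 intervals and any model-based variance carried into the sizing of a later trial.

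**Working it through.** **Inputs.** From the documents: 60 participants allocated equally, so 20 per arm; alpha 0.05 two-sided; and, from section 4.4, "We expect that the true rate of completion of the T3 assessment is 80" per cent. T3 is week 8 in the model's coding. Section 4.2.a attaches both 80% and 75% to week 8, so both are used. Assumed, because the documents give neither: all correlations and SDs.

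**The plan's own figures.** There is no Aim 2 variance, correlation or power figure to reproduce. The T3 completion figure does reproduce: the chance of at least 45 of 60 at a true rate of 80% is 0.869, against 87% stated.

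**1. Precision.** Take SD 1, equal correlation ρ, week-8 completion c, and ignore week-4 values. For one pair of arms at week 8:

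- Planned variance = 2[(1−ρ²)/(20c) + (1−ρ)²/20].
- T1-adjusted variance = 2(1−ρ²)/(20c) × [1 + 1/(60c−5)]. The last factor is the cost of estimating the baseline slope with three arms.

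For ρ = 0.5 and c = 0.8, planned = 2[0.75/16 + 0.25/20] = 0.11875 and adjusted = 2(0.75/16)(1 + 1/43) = 0.09593. The saving is 19.2%.

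| ρ | Completion | Planned | Adjusted | Saving |
|---|---|---|---|---|
| 0.5 | 100% | 0.10000 | 0.07636 | 23.6% |
| 0.5 | 80% | 0.11875 | 0.09593 | 19.2% |
| 0.5 | 75% | 0.12500 | 0.10250 | 18.0% |
| 0.9 | 100% | 0.02000 | 0.01935 | 3.3% |
| 0.9 | 80% | 0.02475 | 0.02430 | 1.8% |
| 0.9 | 75% | 0.02633 | 0.02597 | 1.4% |

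The large-sample, complete-data limit is (1−ρ)/2, that is 25% and 5%. REML simulations at 80% completion gave savings of 18-19% at ρ = 0.5 and 1.5-3.5% at ρ = 0.9.

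**2. SEs when correlation decays and variance is constant.** Let r be the correlation between adjacent visits and r13 that between baseline and week 8. With complete data the random-intercept fit uses the average correlation (2r + r13)/3. The ratio of model to true variance is then [1−(2r+r13)/3]/(1−r13) for the week-8 change, and the same numerator over (1−r) for the week-4 change. For 0.70/0.65 the week-8 ratio is 0.31667/0.35 = 0.905, and its square root is 0.951.

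The rejection rates below come from 40,000 simulated trials per case with complete data and no true effect.

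| r / r13 | Week-8 SE, model/true | Week-4 SE, model/true | Week-8 type I error | Week-4 type I error | Joint 4-df test |
|---|---|---|---|---|---|
| 0.70 / 0.65 | 0.95 | 1.03 | 6.4% | 4.4% | 5.1% |
| 0.80 / 0.75 | 0.93 | 1.04 | 6.8% | 4.1% | 5.1% |
| AR(1), 0.50 / 0.25 | 0.88 | 1.08 | 8.2% | 3.4% | 5.4% |
| AR(1), 0.90 / 0.81 | 0.83 | 1.14 | 10.0% | 2.5% | 6.1% |

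With three equally spaced visits and complete data, the linear slope is the week-8 change rescaled. Its error rates (6.5% to 10.3% in these cases) are therefore not a second finding.

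**3. SEs when variance changes.** The fit in effect averages the three pairwise difference variances.

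- Equal correlation 0.9, SDs 1, 1.2, 1.4: the differences have variances 0.280 (baseline to week 4), 0.376 (week 4 to week 8) and 0.440 (baseline to week 8), with average 0.365. The SE ratio at week 8 is √(0.365/0.440) = 0.91, too small without any decay.
- Equal correlation 0.9, SDs 1, 1.2, 1: variances 0.280, 0.280, 0.200, average 0.253. The ratio is √(0.253/0.200) = 1.13, too large.
- Correlations 0.80/0.75, SDs 1, 1.2, 1: variances 0.520, 0.520, 0.500, average 0.513. The ratio is 1.01, so here decay is present and the week-8 SE is about right.

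**4. The remedy.** Eleven correlation patterns were simulated with 4,000 trials each, SD 1, dropout completely at random, and 90% (assumed) and 80% completion at weeks 4 and 8. An unstructured covariance with the planned means and Kenward-Roger degrees of freedom gave week-8 type I error of 4.5% to 5.4%. Its intervals were 1.3% wider than planned under equal correlation. With T1 adjustment as well, type I error was 4.7% to 5.3%, and half-widths relative to the planned model were 0.911, 0.979 and 1.002 at equal ρ of 0.5, 0.8 and 0.9.

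**The case against.** The strongest reply is that nothing in the documents shows harm. No correlation or SD is given. If both are constant over visits, the planned SEs are correct and only precision is lost, which at ρ = 0.9 is almost nothing. The plan targets change over time and the asthma control threshold applies to change, so a change contrast is a legitimate choice. The tests are hypothesis-generating, raw SDs are also planned, and n = 60 rests on Aim 1. All of this stands. It limits the importance of the point but does not remove the available gain.

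A reader might infer more than the documents support in four ways.

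- That the planned estimate is biased. It is not, under randomization.
- That the SEs are too small, or that decay is what decides it. Step 3 shows that decay is neither necessary nor sufficient.
- That the autoregressive GPS model shows that the sponsor expects decay here. That model is for daily data and says little about visits four weeks apart.
- That a later trial will be mis-sized. This follows only if the model-based variance is used. Under the decay cases in step 2 the variance of the week-8 change is understated by 10-13% (mild) or 22-32% (AR(1)). Sampling error alone gives a variance on 45 degrees of freedom a 95% interval of −31% to +59%.

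**Conclusion.** The point holds as a modest, inexpensive improvement to the analysis of continuous Aim 2 outcomes. Adjusting for T1 would save about 18-24% of the variance of the week-8 contrast at an assumed correlation of 0.5 and about 1-3% at 0.9, depending on completion. The model-based SEs are assured only when correlations and variances are both constant over visits. If variance is constant and correlation decays, the week-8 SE is 5-7% too small under mild decay and 12-17% under AR(1), the week-4 SE is too large, and the joint interaction test stays near nominal (at most 6.1% in the cases shown). If variance changes, the error can go either way. Logit-link outcomes, the GPS model and Aim 1 are outside this conclusion.

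**What to change.** In section 4.4, for identity-link outcomes:

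1. Replace the random intercept and variance components with an unstructured within-person covariance, fitted by REML with Kenward-Roger degrees of freedom. This alone removes both restrictions and can keep the planned means.
2. Estimate the group differences at weeks 4 and 8 adjusted for T1. Either use T1 and T1-by-time as covariates, or keep T1 as a response with a mean common to the arms.
3. Still report within-arm change from baseline, so that it can be set against the MID.
4. Report the estimated variances and correlations beside the raw SDs, for use in sizing a later trial.

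The cost is SAP wording and a changed model statement, with no new data.

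- Covariance parameters rise from 2 to 3 with T1 as a covariate, or to 6 with T1 as a response at three visits. If the T4 assessment named elsewhere in section 4.4 enters the model, T1 as a response needs 10.
- At 80% completion, degrees of freedom fall from about 96 to about 45-52.
- If the planned means are kept and correlation and variance are constant, intervals are about 1% wider.
- If they are not constant, week-8 intervals may be wider, and correctly so. In the AR(1) simulations the T1-adjusted intervals ranged from 5% shorter to 17% wider than the planned ones.
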